### 1.2. Title of the study

HCV micro-elimination in the MSM community

### 1.3. Code of the protocol

MSM-HCV-MicroElimination

### **1.7. Primary objective**

Determine the prevalence of acute and chronic HCV infection in HIV-uninfected MSM and TGW community. Serologic prevalence will also be determined.

Establish a fast-track circuit between Sexual Health Community centers and Hospital liver/infection diseases units to offer the possibility of starting treatment quickly after diagnosis and confirmation of HCV viremia on same day.

### **1.8. Design**

Observational study

### **1.9. Study pathology**

Hepatitis C virus (HCV) infection

### **1.10. Type of population and number subjects**

Men who have sex with other men or transgender women, that are HIV negative and comes to get tested in our center or are under controls in our center.

Estimated enrollment first Phase 6000-7000 participants. Second phase 2000-3000 participants.

### **1.11. Calendar**

- Ethics Committee application: June 2021
- Study starts (first patient in): June 2021
- Recruitment period: 2 years and 2 months.
- Patient follow-up: Single visit. Screening. In case of positive HCV viremia, 6 and 12 months post treatment control will be offered.
- Final report: 2023. Reinfections will be reported during 2024.

### **1.13 Financing source**

- Gilead Sciences
- Cepheid

### **3. GENERAL INFORMATION**

#### **3.1. Code**

MSM-HCV-MicroElimination

#### **3.2. Title**

HCV micro-elimination in the MSM community

#### **3.6. Expected study duration**

The duration of this study is planned to be 2 years June 2021 to July 2023.

Following see the expected study calendar:

- Ethics Committee application: June 2021
- Study start (first patient in): June 2021
- Recruitment period: 2 years and 2 months
- Patient follow-up: Single visit on Screening. In case of positive HCV viremia, 6 and 12 months post treatment control will be offered.
- Final report: End of 2023. Reinfections will be reported during 2024.

## 4. RATIONALE

### Background and Significance

Since 2000, there have been multiple reports of outbreaks of sexually transmitted acute hepatitis C virus (HCV) infection in HIV-positive men who have sex with men (HIV+ MSM) in urban areas of North America, Europe, Australia and Asiai. Acute HCV infection is more likely to become persistent in the presence of HIV, and liver fibrosis progression in chronic HCV infection is faster even in patients with undetectable HIV viral loadsii. At 2018 CROI meeting in Boston the Swiss HCVree trial suggested that offering HCV treatment to all diagnosed HIV/HCV coinfected individuals within the Swiss HIV Cohort may be successful in reducing new incident infections by almost 50% as well as reducing the burden of chronic HCV by over 90%iii. Similar results had been reported at 2017 CROI in Seattle where again an increased uptake of DAA therapy in Netherlands with over 75% of all HIV/HCV coinfected MSM being cured caused a reduction in new infections by around 50% ivvvi. Thereby, these studies indicate that HCV micro-elimination may be achievable in well-identified patient populations. However, the challenge to overcome is the high risk of reinfection in a small number of subjects with very high-risk sexual practices, among HIV coinfected MSM, with reinfection rates of almost 25% after two years of follow-up after a first resolved or successfully treated episode of acute HCVvii.

A potential source for HCV transmission may also come increasingly from HIV-negative MSM. Various studies presented at CROI 2018 looked at HCV prevalence and incident infections in HIV-negative MSM entering PrEP studies showing that the acute HCV epidemic has now also reached the HIV-negative MSM populationviii ix, x. Clearly, early treatment of acute HCV will become crucial for achieving micro-elimination to limit transmission possibilities. Data from the NEAT-ID foundation PROBE-C cohort looked at the natural course of acute HCV infection in HIV-coinfected individualsxi, and only 11% of all patients were able to clear HCV infection spontaneously, which implies that an overwhelming portion of patients will go on to develop chronic HCV infection and require treatment. Early intervention appears advisable to prevent further onward transmission of HCV. However, there is a huge gap as for data and awareness in this population.

## 5. OBJECTIVES

### 5.1. Hypothesis

A community center for MSM and TGW, with a longstanding experience of early HIV detection, linkage to care and treatment initiation, might be able to create a model with low barrier for Point-of-Care (POC) HCV detection in an understudied population. Through a simple algorithm to achieve detection, confirmation, and treatment initiation at the same day, it would be able to achieve rapid HCV viremia suppression in this scenario. Moreover, this model will be replicable in other European cities, where similar community centers and POC technology are in place.

### 5.2. Objectives

The primary Goal of this project is to identify HCV acute and chronic infections in HIV-uninfected MSM and TGW community and to offer them a low barrier linkage to care in the context of a fast-track circuit, offering a first visit with a specialist and starting hep C treatment in the same day after confirmation. A total of 10-15 unknown HCV infections are expected to be diagnosed during the study and to be treated. Potential risk factors for increased HCV infection rates include recreational drug use, including "chemsex", PrEP use, sex work, and several sexual behaviors. We will analyze which factors entangle an increased infection risk. This will allow us to focus and intensify screening on people with these factors while reducing the costs of continuous HCV screening in people who maintain at high risk.

#### Primary objectives

- Determine the prevalence of acute and chronic HCV infection in HIV-uninfected MSM and TGW community. Serologic prevalence will also be determined.
- Establish a fast-track circuit between Sexual Health Community centers and Hospital liver/infection diseases units to offer the possibility of starting treatment quickly after diagnosis and confirmation of HCV viremia on same day.

#### Secondary objectives

- Characterization of risk factors associated with acute and chronic HCV infection in the MSM and TGW community to inform which individuals will benefit more from HCV screening.
- Creation of an HCV pre-test Score during Phase 1 and validation during Phase 2.
- Evaluate user's satisfaction with HCV testing using Patient Reported Outcome Measures (PROMs).
- Evaluation of causes for treatment delay and/or loss to follow up.
- Evaluation of reinfections after treatment during first year post treatment.

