**Table 1. Study Chronogram Phase 1**

	SCREENING	6 months Post Treatment visit*	12 months Post Treatment visit*
Informed consent	X		
Selection Criteria	X		
SD BIOLINE HCV assay	X		
Cepheid "Xpert® HCV VL Fingerstick"	a X	a X	a X
Xpert® HCV Viral Load	b X		
Routine Serology	c X		
genotype study/Hematology and biochemical analysis	d X		
Sexual behavior & demographics questionnaire	X		
PROMS questionnaire	X	X	X

- a) The participants that obtain a positive result from the SD Bioline HCV assay test will be confirmed with Cepheid "Xpert® HCV VL Fingerstick" to identify HCV viremic cases. Also first 1000 participants with a negative result from the SD Bioline HCV assay test that fulfills criteria mentioned on 1B point, will be confirmed with Cepheid "Xpert® HCV VL Fingerstick" to identify acute HCV infections. \*During V6MPTV and V12MPTM the fingerstick will be offered to all the participants with HCV infection detected during the screening visit.
- b) Acute infections with negative antibodies will be also tested with (Cepheid "Xpert® HCV Viral Load) to confirm viremic cases.
- c) In case of positive serology with negative viral load, standard lab serology will be performed to confirm serology, through standard hospital lab circuit.
- d) For the confirmed HCV Viremic cases, it will be analyzed the following parameters: blood count, Serum Creatinine, AST, ALT, GGT, alkaline phosphatases, direct and indirect Bilirubin, prothrombin time and the genotype study will be performed.

*\* Visits after 6 months and 12 months are optional and only are applicable for those patients that had been diagnosed and treated for HCV infection during the screening visit.*

After one year, a statistical analysis (interim analysis at 6 months\*) of the results will be made to determine associated factors for positive antibody test as well as for positive acute HCV test to set selection criteria for phase 2 of the study. A Draft of HCV pre-test Score will be developed with this first-year analysis and implemented during second phase.

\*Interim analysis will be used to evaluate data collection, correct incidences and to set up data analysis system. This will facilitate the results evaluation at the end of Phase 1 and it will allow to create the pre-test score to start the study Phase 2.

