## Phase 2: Targeted testing

During the second year, selected criteria from pre-test score will be used to offer clients an HCV rapid antibody test "SD BIOLINE HCV assay". Estimation of tests: 2,000-3,000. Depending on the results obtained on the first year, this analysis could change.

In addition, about 300 participants that complies the SCORE criteria founded during phase 1 for acute HCV infection, will be performed Cepheid "Xpert® HCV VL Fingerstick". On Visits V6MPT and V12MPT, screening will be performed with Cepheid "Xpert® HCV VL Fingerstick".

The goal with both detection strategies is to uncover a 3-time higher prevalence rate, according to our experience with HIV criteria obtained after evaluation of factors.

Procedures in case of positive results will be as described on first year phase. Final report will focus on proposing how the model could be replicated in other similar cities and settings.

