**Table 2. Study Chronogram Phase 2**

	SCREENING	6 months visit *	12 months visit*
Informed consent	X		
Selection Criteria **	X		
SD BIOLINE HCV assay	X		
Cepheid "Xpert® HCV VL Fingerstick"	X a	X a	X a
Xpert® HCV Viral Load	X b		
Serology	X c		
genotype study/Hematology and biochemical analysis	X d		
Sexual behavior & demographics questionnaire	X		
PROMS questionnaire	X	X	X

- a) About 300 participants that complies the SCORE criteria founded during phase 1 for acute HCV infection, will be performed Cepheid "Xpert® HCV VL Fingerstick". On Visits V6MPT and V12MPT, screening will be performed with Cepheid "Xpert® HCV VL Fingerstick".
- b) If the Xpert® HCV VL Fingerstick test is positive, and SD BIOLINE HCV assay is negative, a confirmation viral load test will be performed to the participant "Cepheid "Xpert® HCV Viral Load"
- c) In case of positive serology with negative viral load, standard lab serology will be performed to confirm serology, thrown standard hospital lab circuit.
- e) For the confirmed HCV Viremic cases, it will be analyzed the following parameters: blood count, Serum Creatinine, AST, ALT, GGT, alkaline phosphatases, direct and indirect Bilirubin, protrombine time and the genotype study will be performed.

\* Visits after 6 months and 12 months are optional and only are applicable for those patients that had been diagnosticated and treated for HCV infection during the screening visit.

\*\* The selection criteria will be defined according to the pre-test score founded during phase 1.

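### Phase 2 is meant to validate the HCV pre-test score but tests only clients who meet it, so it can measure yield, not missed cases; its 3-fold goal also does not fit 3,000 tests

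*Combined protocol and SAP*

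**What the plan says.** Section 5.2 lists among the secondary objectives: "Creation of an HCV pre-test Score during Phase 1 and validation during Phase 2". The text after Table 1 adds: "A Draft of HCV pre-test Score will be developed with this first-year analysis and implemented during second phase".

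Phase 2 is headed as targeted testing. For antibodies: "During the second year, selected criteria from pre-test score will be used to offer clients an HCV rapid antibody test", with 2,000-3,000 tests expected. For acute infection, the viral-load test goes to "about 300 participants that complies the SCORE criteria founded during phase 1 for acute HCV infection". The footnote to Table 2 says the same of entry: "The selection criteria will be defined according to the pre-test score founded during phase 1". The one numerical target is: "The goal with both detection strategies is to uncover a 3-time higher prevalence rate". The plan leaves itself room ("Depending on the results obtained on the first year, this analysis could change") and states the intended use of the results: "Final report will focus on proposing how the model could be replicated in other similar cities and settings".

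The endpoints in section 8.2 do not mention the score; the nearest is the characterization of risk factors. Section 9 describes a univariate screen at p<0.1 after Phase 1, followed by a Poisson regression adjusted for age and gender. It names no score, cut-off, discrimination, calibration, sensitivity or predictive value.

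**The concern.** A score that decides who is tested raises two questions: how many of those selected are positive, and how many positives are left out. Phase 2 as designed observes only the first. A reader who is told that the score was validated in Phase 2 could reasonably think that both had been answered. That matters if other centers adopt the score to decide whom not to test. Section 5.2 already links the risk factors to focused screening and lower screening costs, and Phase 2 itself uses the score in this way.

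Even the validation that Phase 2 could deliver, the yield, has no endpoint or analysis attached. The 3-fold goal is the only available criterion, and it does not fit the whole range of planned tests.

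**Working it through.** **1. What Phase 2 observes.** Cross-classify clients by score (positive/negative) and infection (yes/no), giving true positives TP, false positives FP, false negatives FN and true negatives TN.

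- PPV = TP/(TP+FP): both terms observed.
- Sensitivity = TP/(TP+FN): FN not observed.
- Specificity = TN/(TN+FP): TN not observed.
- NPV = TN/(TN+FN): neither term observed.

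The planned number of score-negative clients tested is zero. Some clients may meet the antibody score but not the acute score. They get a viral load only if antibody-positive, so this does not recover the acute score's false negatives.

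**2. The plan's own figure.** Section 11.5 expects 305 seropositives at 4.7%. This reproduces at the midpoint of 6,000-7,000 clients: 0.047 × 6,500 = 305.5. The ends give 282 and 329.

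**3. Yield does not determine sensitivity.** Purely as an illustration, assume 2,000 selected, 4,500 not selected and 3-fold enrichment. Then TP = 3 × 0.047 × 2,000 = 282. The same Phase 2 result fits all of these:

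| Assumed prevalence in the untested | FN | Sensitivity | NPV |
|---|---|---|---|
| 0% | 0 | 100% | 100% |
| 1% | 45 | 282/327 = 86% | 99% |
| 2% | 90 | 282/372 = 76% | 98% |
| 4.7% | 211.5 | 282/493.5 = 57% | 95.3% |

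The rows show only that Phase 2 data cannot choose between them; none is a forecast.

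**4. Is the 3-fold goal compatible with the number of tests?** Let N1 be the client base and N2 the number selected. With the same base and prevalence in both years, enrichment = sensitivity × N1/N2. Sensitivity cannot exceed 1, so enrichment ≤ N1/N2.

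| Client base | Most that can be selected for 3-fold (N1/3) | Ceiling at 2,000 tests | Ceiling at 3,000 tests |
|---|---|---|---|
| 6,000 | 2,000 | 3.0 | 2.0 |
| 7,000 | 2,333 | 3.5 | 2.33 |
| 7,581 (2019 attendance, section 7.2) | 2,527 | 3.79 | 2.53 |

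**5. What Phase 1 can supply.** Phase 1A offers the antibody test to all clients, so sensitivity and NPV of the antibody score can be calculated there, in the data used to build it. With about 305 positives the approximate 95% half-width for sensitivity is at most 1.96 × √(0.25/305) = 5.6 percentage points. The target is seropositivity; section 11.5 says the viremic share is unknown.

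The acute score has no such source. Phase 1B viral-load testing is limited to 1,000 antibody-negative clients with listed risk criteria, and 10-15 cases are expected over the whole study (called unknown infections in section 5.2, acute in 11.5). Even with everyone tested, 12 of 15 detected would give an exact 95% interval of 52-96%, and 8 of 10 would give 44-97%.

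**6. Size of optimism, under assumptions.** A simulation used independent binary factors, selection at p<0.1, then logistic regression.

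- Antibody score: 6,500 clients at 4.7%, 15 or 30 candidates, 5 real with odds ratio 2 or 3, top 2,000 selected. Apparent sensitivity exceeded true sensitivity by 0.5-2.7 points on average. True sensitivity was 54-70%, an enrichment of 0.54 × 6,500/2,000 = 1.8 to 0.70 × 6,500/2,000 = 2.3.
- Acute score: 1,000 clients, 10 or 15 expected events, all assumed to arise in Phase 1B. The excess was 15-32 points.

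Section 9 plans Poisson rather than logistic regression, so these sizes are indicative only.

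**The case against.** The strongest reply is that the plan never defines validation and never promises sensitivity or NPV. Its one stated criterion is the 3-fold goal, which is a yield, and Phase 2 can measure it. The risk-factor objective, to learn who gains most from screening, also fits yield. This stands as far as it goes: on that reading Phase 2 can test the score's main purpose. But the objective's wording is then too broad, and the yield analysis is still missing from sections 8.2 and 9.

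The plan also calls the score a draft, says the Phase 2 analysis may change, and notes yearly serology in PrEP users. None of these plans testing of score-negative clients or ties existing results to validation.

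It is fair, too, that the model to be replicated is described in section 5.1 as point-of-care detection with same-day treatment. That other cities would use the score to leave clients untested is partly inference.

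Three stronger readings are tempting and are not supported:

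- A reader might infer that the score will miss a particular share of infections. The documents do not fix that share. Figures built on 3-fold enrichment are illustrations, and the simulated scores did not reach 3-fold.
- A reader might infer that the 3-fold goal is impossible. The ceiling does not exclude it near 2,000 tests.
- A reader might infer that the prevalence estimates are compromised. Phase 1A offers testing to all clients, and no primary estimate relies on the score.

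**Conclusion.** The point holds and should be fixed. As written, the plan cannot deliver the promised Phase 2 validation beyond yield, its ratio to Phase 1 and performance within the score-positive range. No analysis is specified even for these. This conclusion follows from who is tested and does not depend on any assumed prevalence.

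The conflict with the 3-fold goal does rest on assumptions: stable prevalence and a stable client base. Under them, 3-fold requires selecting at most 2,000-2,333 of 6,000-7,000 clients, and 3,000 tests allow at most 2.0-2.33-fold. Using the 2019 attendance of 7,581 as the base, although it is unclear which body that count describes, raises the ceiling only to 2.53-fold.

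The consequence is limited to one secondary objective.

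**What to change.** 1. **Objective and goal.** Restate the objective as creation of the score in Phase 1 and evaluation in Phase 2 of the yield of score-targeted testing and its ratio to Phase 1. Reconcile the 3-fold goal with the 2,000-3,000 tests, for example by stating the share of clients to be selected.
2. **Section 9.** For the antibody score, add a Phase 1A analysis of discrimination, calibration, and sensitivity and NPV at the chosen cut-off. Correct for optimism by bootstrap, repeating the p<0.1 selection in every resample, and label the result internal validation. State that the sensitivity and NPV of the acute-infection score are not validated.

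The cost is a protocol and SAP amendment, with Ethics Committee approval since an objective changes, and some added analysis of data already planned. The resulting claim is less favourable than a validated score.

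Two additions are optional:

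- An indirect Phase 2 sensitivity would need scores on clients who are not enrolled, which may raise consent and data-protection questions. It also needs stable prevalence, which is doubtful after a year of screening and treatment in the same centers.
- Antibody-testing a random sample of score-negative clients would give direct evidence on seropositivity only. With 500 tested and no positives, the exact 95% upper limit for missed prevalence is 0.74%. It would change the Table 2 selection criteria and need its own ethics review and consent.

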## 6. INFORMATION SOURCE AND FIELD

Source documents are the patient's medical records.

Study data will be collected through integrated forms in Salus (QSOFT, Software Salus 2017) that is software to compile user's information used in sites participating in this study. It is allocated in a Secure Server according to Personal Data protection Laws.

During the screening visit, the investigator will provide the participant the informed consent and will let the necessary time to read and understand the study procedures. If the participant agrees to participate in the study, he will sign the consent. One copy of the signed IC will be facilitate to the participant.

A demographics and a sexual behavior questionnaire will be requested to be completed by the study participants at the screening visit (See Appendix 2). Additionally, at the end of each study visit, PROMs questionnaire to evaluate satisfaction will be carried out (See appendix 3)(*In this study and adaptation of SUCE questionnaire will be performedxi*).

Additionally, and in case to be necessary it will be asked to the participant information related to previous HCV infections or in case of a diagnostic to follow treatment received and results of blood test performed on other public health units of Catalonia.

The study visits will be performed in the clinical installations of BCN CheckPoint or BCN PrEP·Point, allocated in Barcelona [name] respectively.

### Laboratory determinations

Point of care test (POCT) will be performed in BCN Checkpoint and BCN PrEP·Point.

Whole blood antibodies will be tested with POCT using immunochromatographic rapid test (Abbott rapid HCV test "SD BIOLINE HCV assay"). Viral load to screen and confirm will be performed with whole blood by Point of Care Real-Time Quantitative Reverse Transcription PCR (Cepheid "Xpert® HCV VL Fingerstick"), genotypes 1-6 are covered by this technique, and its limit of detection is 35 IU/mL.

Acute infections with negative antibodies will be also tested with (Cepheid "Xpert® HCV Viral Load), genotypes 1-6 are covered by this technique and its limit of detection is 4.0 IU/mL in plasma and 6.1 IU/mL in genotype 1.

Chemistry and Microbiology HUGTiP laboratories will be used for genotype study and hematology and chemistry evaluation in case of a confirmed diagnostic (positive viral load). Exam will include blood count (3mL EDTA tube), Serum Creatinine, AST, ALT, GGT, alkaline phosphatases, direct and indirect Bilirubin (5mL SST gel Tube), Prothrombin Time (2.7mL coagulation tube) and for the HCV Genotype (10 mL EDTA tube). A total of 20.7mL will be obtained per venipuncture

Microbiology HUGTiP laboratories will be also used for the cases that positive serology is obtained with rapid test and viral load is negative, without having received previous treatment for HCV or without previously known infection, to

confirm possible cases of spontaneous Cure. In these cases, a total of 7mL (SST gel tube) will be obtained by venipuncture.

